changes in visual perception. Although three patients had post-operative local wound infections, no other behavioral or medical adverse events were noted.

This pilot study supports the hypothesis that high-frequency DBS in Cg25 white matter can be used to treat depression, but further data is needed to confirm these findings. We propose a replication study at Emory University that will help further test the efficacy, safety and potential mechanisms of action of DBS for treatment-resistant depression (TRD).

OBJECTIVES

We propose to test whether high frequency DBS of the subgenual cingulate white matter (Cg25-DBS) is a safe and efficacious antidepressant treatment in forty TRD patients, and to investigate potential mechanisms of action of this intervention.

Importantly, this study will be used to assess the need for and assist in planning a larger, more definitive trial of Cg25-DBS for TRD. We will address the following specific aims.

Specific Aim 1. To assess the safety and tolerability of acute and chronic Cg25-DBS. Rates of complications (surgical complications, hemorrhage, stroke, infections, and seizures) will be assessed and compared to known rates for DBS surgery in other disorders.

Specific Aim 2. To assess the antidepressant efficacy of active Cg25-DBS in treatment-resistant depressed patients. We hypothesize that 24 Weeks of open Cg25-DBS will yield statistically significant antidepressant effects.

Specific Aim 3. To assess the possible mechanisms mediating Cg-25 DBS effects on depression. This will include behavioral and psychophysiological measures of emotional response and perception, motor activity and electrophysiological measurements with acute intra-operative testing of DBS.

Secondary Aim 1. To assess long-term effects of Cg25-DBS in patients with Major Depressive Disorder. Patients will be followed naturally over 10 years.

Secondary Aim 2. To assess for variables that predict antidepressant response, remission and relapse over time.

Secondary Aim 3. Changes in mood and behavior associated with DBS will have both immediate effects and slowly evolving, delayed effects, our experimental protocol will assess mood and behavior at several time points post-surgery. This will include behavioral and psychophysiological measures of emotional response and perception, motor activity and electrophysiological measurements.

PROTOCOL

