 - 3.3.5 Magnetic Resonance Imaging (MRI)(60 minutes). This pre-operative scan will help rule out intracranial abnormalities that might explain the patient's level of treatment resistance or preclude the patient from surgery. During this scan, we will also acquire diffusion tensor imaging (DTI) to assess white matter tract integrity and resting BOLD functional MRI data to assess regional connectivity.
 - 3.3.6 Neuropsychological testing (4 hours). A comprehensive neuropsychological battery will be administered by a trained psychometrist under the supervision of a board-certified neuropsychologist. This battery will take approximately 4 hours to

complete but can be done over more than one day if needed to prevent patient fatigue. The study will be performed prior to surgery and repeated at the end of 6 months of active stimulation

3.3.7 **Behavioral Activation:** In an effort to provide rehabilitation to our patients, behavioral activation therapy will be performed. There will be 2-4 sessions pre-op to establish a relationship with the patient. Therapy will begin post operatively when stimulation is started and will occur weekly for approximately 30 weeks.

3.4 **Mechanism of Action Studies.** To help assess mechanism of action (MOA) of DBS for TRD, several MOA experiments will be performed throughout the study beginning in the pre-operative evaluation period. All of the following will be repeated 1 month after surgery during acute DBS testing and again after 1,3, and 6 months of active DBS. :

3.4.1 **Emotional response testing with psychophysical measures.**

Eye-Tracking and Pupilometry: Eye-tracking will be used to measure the visual attention of the participant. The participant sits in front of a computer monitor and simply watches as pictures or sounds are presented. While they view the image or screen, a light beam is used to track the position and size of the pupil and cornea over time in order to estimate position of gaze.

3.4.1.1.1 *Emotional Pictures:* Emotional pictures will be selected from the International Affective Picture System, a standardized, widely available dataset, normed for content and emotional valence (IAPS; Lang, Bradley, and Cuthbert, 2008).

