3.4.2.2 GPS logging. We also hypothesize that decreased depressive symptoms will be associated with an increase in patients' average level of daily life activities including amount of travel outside the home. This will be assessed by a wristband-style GPS route logger, which periodically logs the individual's GPS location, forming a connected route map of daily travels.

3.4.2.3 Security. Patients will be fully informed about the nature of the information that will be recorded, its purpose and use, and will be able to stop, pause, or start the GPS logging function whenever they wish, by pressing a button (patients will receive training on these functions). The GPS logging information will be securely transmitted to a cloud server that will store the route logging information associated with a random study identification number, not the individual's name or other identifying information. The information on the server is only retrievable using a login and password. The route logging information will be used to determine

the number, length, and complexity of travel outside the home.

3.4.2.4 Gait Assessment. We hypothesize that decreased depressive symptoms will be associated with increased gait speed and endurance. Patients will engage in a self-paced walk for six minutes while wearing sensors attached to the trunk and limbs (APDM Wearable Technology).

3.4.3. Electroencephalography. (EEG) (1 hour). This data will be tested in conjunction with the resting bold fMRI as a predictive biomarker of antidepressant response to chronic DBS and as an index of ongoing brain changes with short term and chronic DBS. This study will be performed at baseline, 1 month after surgery and during acute testing of optimal DBS contacts, after 1, 3 and 6 months of active DBS, and at one time point during the naturalistic follow up phase.

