9.2.3 **Specific Aim 1.** We will record all surgical complications in addition to any other adverse events in order to get a reasonable estimate of the risks of the treatment. We will examine specific complication rates in addition to rates of "any" adverse event. We will separately document serious adverse event rates. If possible, we may also do a formal statistical comparison of these sample rates to those associated with DBS surgery in other disorders to determine if the sample rates are comparable. Rates of the first occurrence of all adverse events and device and procedure related adverse events within 24 Weeks following the initial bilateral implants will be summarized along with exact one-sided 95% upper confidence bounds. Similar analyses will be conducted for serious adverse events.

9.2.4 **Specific Aim 2.** We will estimate of the 24 Week response and remission rates; we will quantify the magnitude of the response using repeated measures analysis of variance on the depression scores (HDRS-17) comparing the levels at baseline with those after 24 Week of open DBS treatment.

9.2.5 **Specific Aim 3.** This aim is exploratory and will assess for intraoperative electrophysiological changes associated with stimulation at specific DBS contacts.

9.2.6 **Secondary Aim 1.** The purpose of this maintenance phase will be to attempt to quantify the level of treatment (dose) that is sufficient to sustain the antidepressant effect.

9.2.7 **Secondary Aim 2.** Analyses will include evaluating a variety of measures, including demographics, clinical characteristics, brain morphology and cognitive function, as possible mediators of the antidepressant effect over time. This will be formally carried out in two ways: 1) by comparing these measures in 6 month responders and nonresponders using appropriate two-sample tests (e.g, t-tests for continuous data, chi-square for categorical data) and 2) by using longitudinal analysis to see if either baseline measures of these variables or changes in these variables with treatment are significantly associated with the change in depressive symptoms over time. This can be performed using repeated measures analysis of covariance, or more simply, using linear regression predicting the change in depression (pre-post). Given the nature of the study these analyses will be underpowered but will provide useful data for future comparative trials.

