9.2.8 **Secondary Aim 3.** Analyses will evaluate EEG, emotional reactivity and psychophysiological variables over time, as possible mediators of the antidepressant effect. This will be formally carried out in two ways: 1) by comparing these measures in 6 month responders and nonresponders using appropriate two-sample tests (e.g, t-tests for continuous data, chi-square for categorical

data) and 2) by using longitudinal analysis to see if either baseline measures of these variables or changes in these variables with treatment are significantly associated with the change in depressive symptoms over time. This can be performed using repeated measures analysis of covariance, or more simply, using linear regression predicting the change in depression (pre-post). Given the nature of the study these analyses will be underpowered but will provide useful data for future comparative trials.

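### Section 3.4.3 promises a test of EEG with resting fMRI as a predictive biomarker of response, but sections 9.2.7 and 9.2.8 plan only association analyses, which cannot show prediction

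*Combined protocol and SAP*

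**What the plan says.** Section 3.4.3 gives the EEG two purposes: to index brain changes during stimulation, and to predict outcome. On the second it says: "This data will be tested in conjunction with the resting bold fMRI as a predictive biomarker of antidepressant response to chronic DBS". The fMRI comes from the pre-operative scan in section 3.3.5, which acquires "resting BOLD functional MRI data to assess regional connectivity". Prediction is also a declared aim. Secondary Aim 2 reads "To assess for variables that predict antidepressant response, remission and relapse over time".

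The analysis plan treats these data differently. Section 9.2.8 begins: "Analyses will evaluate EEG, emotional reactivity and psychophysiological variables over time, as possible mediators of the antidepressant effect". It offers two routes. The first works "by comparing these measures in 6 month responders and nonresponders using appropriate two-sample tests". The second is a longitudinal analysis of whether baseline values, or changes during treatment, are significantly associated with change in depressive symptoms, by repeated measures analysis of covariance or simple linear regression. Section 9.2.7 applies the same two routes to "a variety of measures, including demographics, clinical characteristics, brain morphology and cognitive function".

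Section 9.2.1 adds general provisions: influence checks, nonparametric or exact methods, and multivariate analysis or PCA for multiple measures. Both 9.2.7 and 9.2.8 say that their analyses will be underpowered but useful for later comparative trials.

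**The concern.** The question asked and the analysis planned do not match, in four ways.

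- Resting fMRI is not named in section 9, and no joint EEG-fMRI model is described.
- EEG enters section 9 as a possible mediator, not as a predictor.
- The regression route may use changes during treatment, which are not available before surgery and so cannot predict who will respond.
- No AUC, sensitivity, specificity, accuracy against the base rate, cross-validation or hold-out sample is specified. Any accuracy figure would therefore come from the patients used for fitting, where it is biased upward.

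A difference in group means says that a marker is related to response. It does not say how well an individual's response can be foretold. This holds for one prespecified marker, so it is not a matter of the number of tests. At stake is what later trials can take from this study: as planned, they would get a p-value where they need an estimate of predictive performance.

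**Working it through.** **Inputs.** N = 40 (Objectives). Response rates: 4/6 = 0.67, the planning rate in 9.2.2, gives about 27 of 40; 30%, the success threshold in 9.1.6, gives 12 of 40. A 20/20 split is added as a favourable case. Assumed, because the plan does not state them for these tests: two-sided 0.05, a normally distributed marker with equal variances, and no dropout.

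**The plan's own figure.** Section 9.2.2 says 19 patients suffice to detect an effect size of 0.68. A one-sample (paired) t-test with 18 degrees of freedom and noncentrality 0.68 × √19 = 2.96 has power 0.800, so the figure reproduces as a before-after comparison. It does not carry over to responders against nonresponders: two-sample power at d = 0.68 is about 0.25 for 13/6 (N = 19), 0.50 for 27/13 and 0.48 for 12/28. Neither figure concerns prediction.

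**Smallest significant difference.** d = t(0.975, 38) × √(1/n1 + 1/n2), with t = 2.024.

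**Discrimination.** AUC = Φ(d/√2).

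**Best accuracy.** Let π be the response rate, with unit-variance normals centred at d (responders) and 0 (nonresponders). The optimal cut-off is c = d/2 − ln(π/(1−π))/d. Sensitivity is 1 − Φ(c − d), specificity is Φ(c), and accuracy is π × sensitivity + (1 − π) × specificity. This takes the just-significant difference as the true one and places the cut-off optimally.

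| Responders/nonresponders | d | AUC | c | Sens. | Spec. | Accuracy | Larger group | Gain |
|---|---|---|---|---|---|---|---|---|
| 12/28 | 2.024 × 0.345 = 0.70 | 0.69 | 1.56 | 0.19 | 0.94 | 71.7% | 70.0% | 1.7 points |
| 27/13 | 2.024 × 0.338 = 0.68 | 0.69 | −0.73 | 0.92 | 0.23 | 69.7% | 67.5% | 2.2 points |
| 20/20 | 2.024 × 0.316 = 0.64 | 0.67 | 0.32 | 0.63 | 0.63 | 62.6% | 50.0% | 12.6 points |

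**Regression route.** For one predictor in 40 patients, a just-significant slope corresponds to r² = t²/(t² + 38) = 4.10/42.10 = 0.097. About 10% of the variance in change is explained, again measured in the fitted patients.

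**Precision.** The Hanley-McNeil standard error of the AUC is 0.086 at 27/13, giving 0.69 ± 1.96 × 0.086, or about 0.52 to 0.85. At 12/28 it is 0.097, giving about 0.50 to 0.88. Any estimate of predictive performance from this trial will be wide.

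**The case against.** The strongest reply is that this is a preliminary single-arm study, that the plan calls these analyses underpowered, and that screening for associations to test later is a proper use of two-sample tests and regression. That stands as a description of the study's role, and no primary result depends on this point. But the caveat is about power. It does not supply a measure of prediction for a purpose the protocol itself states.

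Second, the plan's methods are broader than t-tests, and the list in 9.2.7 is open-ended, so it does not exclude resting fMRI. This is also true. Yet PCA and multivariate methods reduce dimensions; none of the listed methods estimates performance in patients not used for fitting.

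Third, raw accuracy against the larger group is a harsh yardstick when groups are unequal. The same marker has an AUC of about 0.69 against 0.50 by chance, the gain at 20/20 is about 13 points, and a marker with a stronger association would do better. This limits the size of the point: the 2-point gain describes a marker at the significance boundary with an unequal split.

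A reader might go further and infer that the trial will call any marker with p < 0.05 a predictive biomarker. The documents do not say so: 3.4.3 says only that the data will be tested. A reader might also infer that inflated AUCs from picking the best of many noise features will be reported. The plan describes no such outcome-driven selection and no classifier, so figures built on that procedure are not evidence about this plan.

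**Conclusion.** The point holds as a mismatch between stated purpose and stated analysis. Sections 9.2.7 and 9.2.8 can show that EEG measures, or other measures, are associated with response. They cannot show that EEG with resting fMRI predicts it, and the joint question in 3.4.3 has no matching analysis at all. At N = 40, significance alone is compatible with a gain of about 2 points over the larger-group rate at either response rate the documents name, and about 13 points at an even split. These sizes rest on the assumed two-sided 0.05 level, normality with equal variances, and complete data. That validation is absent is read from the lack of any such step in the text. The matter is exploratory and leaves the response-rate estimate untouched, but it should be corrected because these results are meant to inform later trials.

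**What to change.** In 9.2.8, add one exploratory prediction analysis of 24-week response from a small, named set of baseline EEG and baseline resting fMRI measures. Use pre-treatment values only, not changes on treatment. Put any feature selection or tuning inside repeated cross-validation. Report the cross-validated AUC with a 95% interval, and accuracy beside the base rate.

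Do not make the biomarker label depend on a permutation test of AUC against 0.5. That is another test against chance, and a marker that adds little over the base rate can pass it. Keep the two-sample and regression analyses, reported as associations. Because every patient receives DBS, describe any marker as a candidate for predicting outcome among DBS-treated patients that needs validation in a later trial.

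The cost is plan wording and some analysis time; no new data, visits or patients are needed. The interval will be wide at this sample size, and the figure will be less favourable than one read from the fitted patients.

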4.0 Surgery

4.1 Target Identification. Patients will come to Emory University Hospital on the morning of surgery. A CRW stereotactic frame (Radionics, Inc., Burlington, MA) will be affixed to the patient's head and preoperative MRI obtained (Signa, 1.5 tesla; General Electric, Milwaukee, WI). The x, y, and z coordinates of the anterior (AC) and posterior commissures (PC) will be determined using axial 3D T1 MR images. To reach the intended target within the subgenual cingulate white matter, a midline T2 sagittal image will be selected and the cingulate gyrus below the genu of the corpus callosum identified. A line will be traced from the most anterior aspect (genu) of the corpus callosum to the anterior commissure and the midpoint selected. The T2 coronal section corresponding to the plane of this midpoint will be identified and the coordinates of the transition point between the gray and white matter identified.

4.2 DBS Surgery. In the operating room under local anesthesia, a burr hole will be drilled 2 cm from the midline immediately anterior to the coronal suture. The underlying dura mater will be opened, and the exposed pial surface coagulated. A mixture of fibrin glue and cryoprecipitate will be used to prevent cerebrospinal fluid egress and minimize brain shift. The CRW arc will be attached to the head frame and set to the pre-determined target coordinates. Micro-electrode recordings will commence at 10 mm above the target using electrodes made from parylene-C-insulated tungsten wires and plated with gold and platinum (FHC, Inc., Bowdoinham, ME). Cellular activity will be amplified (DAM 80 WPI Instruments) with a gain of 1000 and initially filtered to 0.1-10 kHz. The signal will be displayed on an oscilloscope (Axon Instruments) and directed to an audio monitor (Grass AM 8, with noise clipping circuit). Microelectrode mapping will be used mainly to confirm the anatomic location of the gray and white matters of area 25, characterized respectively by the recording of neuronal activity and cell sparse areas. The transition between these two regions will be chosen as the final target for the implantation of the electrodes. DBS quadripolar electrodes (St. Jude Medical Neuromodulation; Plano, TX) will be implanted bilaterally. Each of the 4 electrode contacts will be tested for adverse effects and clinical benefits. These contacts will be numbered from 1-4 (left hemisphere) and 5-8 (right hemisphere), with 1 and 5 being the most ventral and 4 and 8 the most dorsal contacts. The Positive And Negative Affect Scale (PANAS) and visual analog scales will be used to test mood intraoperatively as each contact is tested. This portion of the surgery will be videotaped.

4.3 Intraoperative Recording. We will record electrical activity (single cell recording and local field potentials) in the vicinity of the surgical target and along the electrode trajectory. We will also record scalp EEG, facial EMG,

Skin conductance (SCR), and heart rate intraoperatively.. Recording will occur prior to, during and after stimulation at each DBS contact. This will provide comparable measures to those measured in the lab during the Emotional testing sessions.

5.0 Post-operative care. Prophylactic antibiotics will be administered for 24 hours after the surgical procedures. An 1.5T MRI will confirm DBS electrode placement and absence of intraoperative complications (e.g., intracranial air, hemorrhage, edema). Patients will be discharged 1-3 days following surgery.

6.0 Post-operative, Stimulation Off Phase (4 weeks)

6.1 Patients will be discharged with the DBS system off (patients will be told the system is off).

6.2 Patients will be evaluated weekly for four weeks to assess for behavioral changes following DBS surgery but prior to receiving active, chronic stimulation.

6.3 Clinical Assessments. During this phase, clinical assessments will include:

- 6.3.1 HDRS
- 6.3.2 HAS
- 6.3.3 MADRS
- 6.3.4 YMRS
- 6.3.5 BDI
- 6.3.6 BAI
- 6.3.7 IDS-SR
- 6.3.8 DAS
- 6.3.9 DOTS-R
- 6.3.10 BHS
- 6.3.11 Q-LES-Q (every 4 weeks)
- 6.3.12 HLQ (every 4 weeks)
- 6.3.13 TAS
- 6.3.14 C-SSS
- 6.3.15 SDS
- 6.3.16 PGI-S
- 6.3.17 PGI-I
- 6.3.18 CGI-S
- 6.3.19 CGI-I
- 6.3.20 Medication log

6.4 High Resolution x-ray CT scan: this study will be used to verify the final location of DBS electrode contacts needed for selection of the optimal contact for chronic stimulation.

6.5 Emotional response testing, actigraphy and GPS logging, EEG #2: Patients will return for repeat testing (same as 3.4.1-3).

7.0 Open Stimulation Phase (4-30 weeks post-op)

7.1 Clinical Assessments. During this phase, patients will return every two to four weeks for clinical assessments to include:

- 7.1.1 HDRS
- 7.1.2 HAS
- 7.1.3 MADRS
- 7.1.4 YMRS
- 7.1.5 BDI

- 7.1.6 BAI
- 7.1.7 IDS-SR
- 7.1.8 DAS
- 7.1.9 DOTS-R
- 7.1.10 BHS
- 7.1.11 Q-LES-Q (every 4 weeks)
- 7.1.12 HLQ (every 4 weeks)
- 7.1.13 TAS
- 7.1.14 C-SSS
- 7.1.15 PGI-S
- 7.1.16 PGI-I
- 7.1.17 CGI-S
- 7.1.18 CGI-I
- 7.1.19 Medication log
- 7.2 Behavioral Activation Therapy: Patients will begin BA with the onset of stimulation. There will be a maximum of 30 sessions over the course of the first 6 months.
- 7.3 Emotional response testing #3-4: Patients will return for repeat testing at 1 month and 3 months of DBS. SCR and activity will be monitored continuously for the first month using the Q-Sensor mobile wrist sensor, 3-D accelerometer and Garmin mobile GPS devices. Weekly testing will be performed monthly for months 2-6.
- 7.4 EEG #3 and #4: EEG will be repeated at 1 month, 3 months of DBS.
- 7.5 End of Phase MOA Assessment. At the end of this 24 Week phase, patients will be evaluated as follows (see above for details):
 - 7.5.1 Neuropsychological testing #2
 - 7.5.2 Emotional response testing, actigraphy, GPS logging and EEG #5.
- 7.6 Programming Adjustments. Initial stimulation settings will be 130 Hz, 91 μ s pulse width, 4mA monopolar bilateral stimulation (one contact per electrode array per side). Every 4 weeks, after the clinical evaluation, a decision will be made whether to continue at these settings or make an adjustment. Adjustments will be made based on whether a patient is considered IMPROVED (>10% change in the 17-item HDRS score from the previous assessment and/or at least minimally approved on the CGI-I), UNCHANGED (\leq 10% change in the 17-item HDRS score from the previous assessment and/or unchanged on the CGI-I) or WORSE (>10% increased in the 17-item HDRS score from the previous assessment and at least minimally worse on the CGI-I) using the following algorithm:
 - 7.6.1 If IMPROVED, make no change and re-assess in 4 weeks.
 - 7.6.2 If UNCHANGED or WORSE, go through the following sequence of steps:
 - 7.6.2.1 Increase amplitude to 6 mA and reassess in 4 weeks.
 - 7.6.2.2 Increase amplitude to 8 mA and reassess in 4 weeks.
 - 7.6.2.3 Re-evaluate contact location and consider a contact switch; remain at 8 mA; re-assess in 4 weeks.
 - 7.6.2.4 Re-evaluate contact location and consider adding a second contact; remain at 8 mA; re-assess in 4 weeks.
 - 7.6.3 To date, there has been no association with stimulation of this brain region or increased amplitude of stimulation with a worsening of depression. When patients have had a worsening of

depression, this has consistently been determined to be due to environmental stressors or the natural history of the patient's illness (normal fluctuations). However, if a patient experiences a >30% increased in the 17-item HDRS score within 4 weeks of a stimulation setting change AND there is no other cause identified for this worsening, then the stimulation parameters will be returned to the previous settings and the patient will be re-evaluated in 4 weeks (or sooner if clinically indicated).

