2.1.8.2 Failure or intolerance of an adequate course of electroconvulsive therapy (ECT) **during any episode** (confirmed by medical records), or refusal of ECT due to a reason considered to be valid by the study psychiatrist. Such reasons might include concern regarding the impact of cognitive side effects of ECT on current ability to work or function, or inability to obtain third-party payment for a course of ECT. Additionally, it is recognized that the probability that a patient who has failed four medications in the current episode will achieve a lasting response with ECT is about 18% (60% probability of an acute response and 30% chance of maintaining this for at least 24 Weeks); patients who have refused ECT because this chance of benefit does not outweigh the risks associated with ECT will be considered eligible.

2.1.9 A patient may remain on psychotropic medications during this study. However, doses must remain stable during the 4 weeks prior to surgery, the four weeks post-operatively, and the 24 weeks open stimulation phase. Medications will be changed only if intolerable side effects clearly attributable to the medications develop.

2.1.10 All patients must have an established outpatient psychiatrist and be willing to sign a written release to allow study investigators to give and receive information from this psychiatrist.

2.2 Ineligibility Criteria. Patients will be excluded if they have:

- 2.2.1 Inability to tolerate general anesthesia.
- 2.2.2 Significant cerebrovascular risk factors or a previous stroke, documented major head trauma or neurodegenerative disorder.
- 2.2.3 Other currently active clinically significant Axis I psychiatric diagnosis including schizophrenia, panic disorder, obsessive-compulsive disorder, generalized anxiety disorder or post-traumatic stress disorder. Patients with severe Axis II personality disorders will also be excluded if the personality disorder is likely to interfere with cooperation and adherence to the study protocol.
- 2.2.4 Current psychotic symptoms.
- 2.2.5 Evidence of global cognitive impairment.
- 2.2.6 Substance abuse or dependence not in full sustained remission (i.e., not active for at least one year).

- 2.2.7 Active suicidal ideation with intent; suicide attempt within the last six months; more than three suicide attempts within the last two years.
- 2.2.8 Pregnancy or plan to become pregnant during the study period.

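### In the 24-week open phase, the stimulation algorithm (7.6) has no exception for a stimulation side effect or (hypo)mania, and the medication limit (2.1.9) has none for rescue treatment

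*Combined protocol and SAP*

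**What the plan says.** Section 7.6 of the combined protocol and SAP starts stimulation at 4 mA and takes a decision every 4 weeks. The basis is stated: "Adjustments will be made based on whether a patient is considered IMPROVED", UNCHANGED or WORSE. All three categories are defined from the change in HDRS-17 since the previous assessment and from CGI-I.

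- IMPROVED (7.6.1): "If IMPROVED, make no change and re-assess in 4 weeks".
- UNCHANGED or WORSE (7.6.2): "If UNCHANGED or WORSE, go through the following sequence of steps". The first step is "Increase amplitude to 6 mA and reassess in 4 weeks", the second goes to 8 mA, the third considers a contact switch and the fourth considers a second contact, both at 8 mA.
- Step-back (7.6.3): settings revert "if a patient experiences a >30% increased in the 17-item HDRS score within 4 weeks of a stimulation setting change", provided that no other cause is identified.

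On medication, 2.1.9 requires that "doses must remain stable during the 4 weeks prior to surgery, the four weeks post-operatively, and the 24 weeks open stimulation phase", and adds: "Medications will be changed only if intolerable side effects clearly attributable to the medications develop".

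Patients with bipolar disorder are eligible (2.1.3). YMRS and C-SSS are collected in the open phase (7.1.4, 7.1.14). Programming and medication by clinical judgment are granted in 8.4 and 8.5, which govern the ten-year naturalistic phase.

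**The concern.** Specific Aim 1 is safety and tolerability, yet tolerability is not an input to the rule that sets the stimulation dose. Section 10.1 foresees complications from stimulating neighbouring structures and describes the effects of stimulating this target in depressed patients as largely unknown. Mania is a foreseeable event in a trial that admits bipolar patients. The mania and suicidality scales are collected, but no stated action follows from them.

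At stake is what staff are told to do for an individual patient. Where the written rules point to keeping or raising stimulation, or make a needed drug a departure, staff who do the sensible thing act without a stated basis. The analysis also has no rule for the patients concerned.

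**Working it through.** The plan gives no statistical figure on this point, so the check is to follow the text.

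**The algorithm's range.** Of the four steps in 7.6.2, two raise amplitude (to 6 and 8 mA), two stay at 8 mA, and none lowers it. The one reduction is in 7.6.3. Assuming that the first decision falls 4 weeks after stimulation starts, a patient rated UNCHANGED or WORSE every time reaches 6 mA at week 4 and 8 mA at week 8 (8/4 = 2 times the starting amplitude). The contact-switch step falls at week 12 and the second-contact step at week 16, all within the 24 weeks.

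**Case A: flat mood with a stimulation side effect.** HDRS-17 changes by 10% or less and CGI-I is unchanged, so the category is UNCHANGED and the next step is an increase. The step-back does not apply, because HDRS-17 has not risen by more than 30%. If the clinician marks CGI-I down because of the side effect, the patient still falls under UNCHANGED or WORSE, and both lead upward.

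**Case B: emerging (hypo)mania with a falling HDRS-17.** I read the 10% change in the IMPROVED definition as a fall. For a patient whose previous score is 20 (the entry minimum), 10% is 0.10 × 20 = 2 points, so a fall of 3 points is enough. The result then depends on CGI-I:
- CGI-I at least minimally improved: IMPROVED, so the setting is kept.
- CGI-I unchanged: IMPROVED is met through HDRS-17 and UNCHANGED through CGI-I, because each definition joins its two parts with and/or. The text does not say which prevails, so the setting is kept or raised.

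Neither branch lowers stimulation, and the step-back cannot apply while HDRS-17 is falling.

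**Case C: rescue medication.** The limit in 2.1.9 covers 4 + 24 = 28 weeks after implantation, or 4 + 4 + 24 = 32 weeks with the pre-operative period. Its one exception requires that the problem be intolerable and clearly caused by the medication. Drug-induced (hypo)mania meeting that test is covered. Mania or acute suicidality attributed to stimulation or to the illness is not, so treating it with a medication change is a departure.

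**Search for an exception elsewhere.**
- 10.2 halts the study as a whole on event rates and does not address one patient's settings.
- 10.3.4 has the DSMB review serious events as they arise. Under 10.3.5, hypomania or a stimulation side effect need not be serious.
- The clinical-judgment clauses in 8.4 and 8.5 start after the 24 weeks.
- 9.2.3 and 7.1.19 record adverse events and medications but trigger no action.

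**The case against.** The strongest reply is that 7.6 is an efficacy-titration rule. It does not claim to override ordinary management of adverse events, and it does not forbid holding or lowering amplitude. The decision follows a clinical evaluation that already includes YMRS and C-SSS, and CGI-I is itself a clinician's judgment. Contacts are tested for adverse effects at surgery (4.2), and acute DBS testing follows at 1 month (3.4). Every patient has an outpatient psychiatrist in contact with the investigators (2.1.10), and the DSMB may stop the study at any time (10.3.7). Section 10.1 reports no unanticipated adverse effects in 20 Toronto patients or 23 in this protocol, and 7.6.3 adds: "To date, there has been no association with stimulation of this brain region or increased amplitude of stimulation with a worsening of depression".

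Much of this stands. Clinicians would probably act, and a reader who inferred that the protocol compels escalation in a patient with a side effect, or that patients have been harmed, would go beyond the text: 7.6 is silent on tolerability, and no case is reported.

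It does not close the gap. The clinical evaluation fixes when the decision is made, while the next sentences fix what it rests on. Contact testing precedes the chronic stimulation that the algorithm governs, and the test amplitudes are not given. The outpatient psychiatrist's involvement does not relax 2.1.9. The reassurance in 10.1 concerns unanticipated effects, whereas stimulation of adjacent structures is an anticipated one. The statement in 7.6.3 concerns only worsening depression.

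**Conclusion.** The gap is real and cheap to close. In the 24-week phase the written rules point to raising stimulation in Case A and to keeping or raising it in Case B, and they make the rescue medication of Case C a departure. This rests on following 7.6 and 2.1.9 as written and on the text supplied; consent pages are not available.

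Three stronger inferences are not supported:
- That a patient with (hypo)mania and a falling HDRS-17 is always left unchanged as IMPROVED. The overlapping definitions mean that an increase is also possible.
- That a definite number of patients would benefit. Subtracting the 23 implanted (10.1) from the 40 planned (Objectives) is tempting, but the count of 23 is undated, and the text mixes dates (13 patients in the earlier series in the Introduction, 20 in 10.1). The number is unknown and may be small.
- That the 30% success verdict in 9.1.6 is affected. Nothing in the documents shows this.

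**What to change.** - **7.6:** amplitude is not increased, and may be reduced or switched off, for a stimulation-related adverse effect or emergent (hypo)mania, judged from that visit's YMRS, C-SSS and adverse events.
- **2.1.9:** medication may also be changed when patient safety requires it, for example for emergent mania or acute suicidality.
- **Record:** each exception is noted with its reason.
- **9.1.6:** a patient given rescue antidepressant or mood-stabilising medication before week 24 counts as a non-responder in the success count, with an as-observed sensitivity analysis. Without this rule, a patient who improved on rescue medication could count as a DBS success.

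The cost is a few sentences, a short note per exception and one sensitivity analysis; no new assessments are needed. The downsides are some departures from fixed settings or medication before the endpoint, a possibly slightly lower response rate, and a single-arm cohort treated under two versions of 7.6, since 10.1 shows that implantation has begun.
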